#### b) **Method of treatment assignment**

Single arm patient centered clinical trial

At study entry, participants will consent study participation via daily monitoring and will choose whether to participate in the activity monitoring, cytokine assessment and drug treatment portions of the trial. Participants who do not choose to take fluoxetine will serve as the control subjects. Additionally, patients will have the choice weekly to decide to start, continue, or discontinue the fluoxetine. See figure below :

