#### **d) Justification of the number of subjects**

All power calculations were done with the clincalc program and assume a dichotomous endpoint in a two independent sample study and are based on achieving the standards of a power of 0.80 and with an alpha of 0.05. Please note, that the assumptions of fluoxetine effect size are based on the absolute most conservative values in the published literature reviewed above.

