#### **Aim 1 : Hospitalization rates**

Assumptions:

1. 2/3 of patients who enter the trial will choose to take fluoxetine
2. 10% of COVID-19 + patients will progress to a clinical condition requiring hospitalization
3. Fluoxetine treatment decreases hospitalization rate by 50%

Sample Size : 312 in the no medication group and 624 in the 2 fluoxetine groups, for a total sample size of 936. This sample size is very achievable given the current coronavirus pandemic.

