**f) Primary and secondary outcome measures**

Primary Outcome Measures:

Aim 1 : Rates of Hospitalization

Aim 2 : Rates of Intubation and Death

Aim 3 : Side effect profile

Secondary Outcome Measures:

Aim 1 and 2 : Depression, Anxiety, Suicidal thinking, Days of Illness, Severity of Illness

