#### **4) Planned data analysis**

Aim 1, 2, 3 : Descriptive statistics,

Compare rates of primary and secondary outcome measures in subjects receiving fluoxetine with those not receiving fluoxetine by Student t-test and Chi-square test as appropriate.

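### Student's equal-variance t-test with an expected 1:2 split: for continuous secondary outcomes the true error rate could drift from 0.05 if the two groups' spreads differ materially

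*Combined protocol and SAP*

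**What the plan says.** The inferential plan is one sentence in section 4 (Planned data analysis), beyond a mention of descriptive statistics. The comparison is described as follows: "Compare rates of primary and secondary outcome measures in subjects receiving fluoxetine with those not receiving fluoxetine". The methods for it are given in a single closing phrase, namely "by Student t-test and Chi-square test as appropriate". It does not say which outcome gets which test. It mentions neither a variance check nor an unequal-variance version of the t-test, and it sets no significance level.

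Section 3 f lists the secondary outcomes as "Aim 1 and 2 : Depression, Anxiety, Suicidal thinking, Days of Illness, Severity of Illness". The Procedures table in section 3 h has PHQ-9 and GAD-7 completed weekly, so depression and anxiety would naturally be analysed as scores. The primary outcome for Aim 1 is a rate: "Aim 1 : Rates of Hospitalization". Aim 2 likewise concerns rates, of intubation and death.

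Under section 3 b patients choose their own treatment: "Participants who do not choose to take fluoxetine will serve as the control subjects". They may also start or stop each week. The Aim 1 sample-size section assumes that "2/3 of patients who enter the trial will choose to take fluoxetine", giving "312 in the no medication group and 624 in the 2 fluoxetine groups, for a total sample size of 936". Section 4 compares takers with non-takers, so the two fluoxetine groups count as one group of 624. Section 3 d says the power calculations are "based on achieving the standards of a power of 0.80 and with an alpha of 0.05".

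**The concern.** By its usual meaning, Student's t-test assumes equal variances and pools them. With equal group sizes this does little harm. With a 1:2 split the pooled variance is weighted towards the larger group, whereas the true variance of the mean difference depends more heavily on the smaller one. If the smaller, no-medication group is more variable, the pooled standard error is too small and false positives become more frequent. If the fluoxetine group is more variable, the standard error is too large and power is lost. Enrolling more patients at the same ratio does not remove the error.

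Nothing in the design makes equal spread a safe assumption. The groups are self-selected, so even their baseline variances need not match. The drug is an antidepressant, and two of the listed outcomes are depression and anxiety, so it could change the spread of those scores as well as their mean. At stake are the p-values and confidence intervals for continuous secondary outcomes, such as depression and anxiety scores and days of illness.

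**Working it through.** **1. The plan's own figure.** Inputs from the Aim 1 section: 10% hospitalised without medication, 5% with fluoxetine, alpha 0.05, power 0.80, split 1:2. The documents do not state sidedness; two-sided is assumed. The weighted mean rate is (0.10 + 2 × 0.05)/3 = 0.0667. Without continuity correction,

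n₁ = [1.960·√(1.5 × 0.0667 × 0.9333) + 0.8416·√(0.10 × 0.90 + 0.05 × 0.95/2)]² / 0.05² = 311.6,

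which rounds up to 312, with 624 on fluoxetine and 936 in total. This matches the plan exactly. The calculation concerns a binary endpoint, so the choice of t-test does not enter it.

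**2. Error in the pooled standard error.** Take n₁ = 312 (no medication, variance v₁) and n₂ = 624 (fluoxetine, variance v₂).

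- Expected pooled SE² = [(311·v₁ + 623·v₂)/934] × (1/312 + 1/624)
- True SE² = v₁/312 + v₂/624
- R = √(pooled SE² / true SE²)
- True two-sided size ≈ 2 × [1 − Φ(1.960·R)]

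Example with v₁ = 2 and v₂ = 1: the pooled variance is (622 + 623)/934 = 1.3330. Pooled SE² is 1.3330 × 0.0048077 = 0.0064085 and true SE² is 0.0080128. So R = 0.894, 1.960 × 0.894 = 1.753, and the size is 0.080.

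**3. Results at 312 vs 624, nominal 0.05.** The variance ratios are assumptions, because the documents give no SD for any score or duration.

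| More variable group | Variance ratio | SD ratio | R | True size |
|---|---|---|---|---|
| No medication | 1.5 | 1.22 | 0.935 | 0.067 |
| No medication | 2 | 1.41 | 0.894 | 0.080 |
| No medication | 3 | 1.73 | 0.845 | 0.098 |
| Fluoxetine | 1.5 | 1.22 | 1.069 | 0.036 |
| Fluoxetine | 2 | 1.41 | 1.118 | 0.028 |
| Fluoxetine | 3 | 1.73 | 1.183 | 0.020 |

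Using the t critical value on 934 degrees of freedom instead of 1.960 lowers each size by less than 0.001.

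**4. Small differences.** With control-to-fluoxetine SD ratios of 0.9 and 1.1, R is 1.036 and 0.969, and the size is 0.042 and 0.058.

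**5. Equal groups.** With 468 per group, R is 1.000 and the size is 0.050 at every SD ratio tried, from 0.5 to 2. The problem therefore needs both unequal group sizes and unequal spread.

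**6. Simulation, 40,000 normal-data runs per setting.** With the no-medication variance 1.5, 2 and 3 times larger, Student's test rejected at 0.067, 0.080 and 0.099, and Welch at 0.050, 0.051 and 0.050. With the fluoxetine variance larger by the same factors, Student's rejected at 0.037, 0.029 and 0.020, and Welch at 0.051, 0.050 and 0.049. With skewed (gamma) data, Welch stayed at 0.049 to 0.054 for SD ratios from 0.5 to 1.5 and reached 0.057 at 2.

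**7. Price of Welch if the variances are equal.** At a true difference of 0.2 SD, simulated power was 0.8226 for Student's test and 0.8222 for Welch.

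**The case against.** The strongest reply is that the effect is hypothetical and narrow. No standard deviation is given, so neither the size nor the direction of any difference in spread is known. A variance ratio of 3 may never arise. The 1:2 split is an assumption about uptake, and weekly switching leaves the realised sizes open; at equal sizes the problem vanishes. Section 4 never uses the word pooled, never assigns the t-test to particular outcomes, and is too brief to show that an unequal-variance version is excluded. The 0.05 level is stated for power calculations on a binary endpoint, and no level is set for the secondary comparisons. The Aim 2 sample-size text also describes the study as a pilot.

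Most of this stands and limits the point. It does not remove it. The phrase about appropriateness most naturally chooses between the t-test and chi-square, and the t-test that is named is the equal-variance one. The 1:2 split is the only one the plan works with.

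A reader might infer that any difference in spread breaks the 0.05 level, or that the plan will produce excess false positives. The documents support neither. SD ratios near 1 leave the size practically nominal, and in one of the two directions the test is merely conservative.

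A further objection is that Welch would not make these comparisons sound, because self-selected groups that can switch weekly are compared without adjustment. That is correct, and it is the larger problem.

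**Conclusion.** The point holds as a small refinement. Section 4 names the equal-variance test where the plan's own expected group sizes remove that test's protection against unequal spread. For any secondary outcome analysed as continuous, the true size of a nominal two-sided 0.05 test could be about 0.067 to 0.098 if the no-medication group is the more variable, or 0.036 to 0.020 with lost power if the fluoxetine group is. These figures assume variance ratios of 1.5 to 3 and realised sizes of 312 and 624. For SD ratios between 0.9 and 1.1 the effect is negligible.

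It would be wrong to read this as a flaw in the primary analysis. Hospitalisation, intubation and death are rates, for which chi-square is the natural choice of the two named tests, and the total of 936 is unaffected. It would be equally wrong to conclude that changing the t-test makes the group comparison valid: confounding from self-selection and weekly switching remains in full.

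**What to change.** In section 4, replace Student's t-test with the Welch (unequal-variance) t-test for secondary outcomes analysed as continuous, and report each mean difference with its Welch 95% confidence interval. Naming the test beforehand also removes a choice that could otherwise be made after seeing the data. Section 4 plans no regression, so no wording on robust standard errors is needed for this point.

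The cost is a change of wording and a software option. No extra data or patients are required, the sample size stands, and the power loss under equal variances is negligible. Confounding needs its own remedy and should not be treated as settled by this change.

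### The planned comparison of depression and anxiety scores gives the entry score no role, so an entry difference between people who choose fluoxetine and those who decline could appear as, or mask, a drug effect.

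*Combined protocol and SAP*

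**What the plan says.** Section 3(f) lists the secondary outcomes as "Aim 1 and 2 : Depression, Anxiety, Suicidal thinking, Days of Illness, Severity of Illness". The Procedures table in section 3(h) schedules the PHQ-9 and GAD-7 at study entry and weekly after that.

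The groups are formed by choice. Section 3(b) states: "Participants who do not choose to take fluoxetine will serve as the control subjects". It also lets each participant take up or stop the drug from week to week.

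Section 4, Planned data analysis, offers descriptive statistics and then one comparative method for all primary and secondary outcomes, between those receiving and those not receiving fluoxetine: "Student t-test and Chi-square test as appropriate". It names no covariate, change score, analysis week, repeated-measures model or method for confounding. Section 3(g) lists demographic and medical variables but gives them no part in the comparison.

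**The concern.** The drug is an antidepressant and these outcomes are depression and anxiety scores, so mood at entry is a plausible reason to accept or refuse it. Nothing in the design balances entry scores. The plan collects the one measurement that would show an imbalance and does not use it.

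Entry and follow-up scores on the same scale are usually correlated, so part of any entry difference carries through to follow-up whether or not the drug does anything. The direction depends on who chooses. If people with more symptoms choose fluoxetine, a comparison of follow-up scores makes the drug look worse or hides a benefit. If people with fewer symptoms choose it, the drug looks better than it is. The documents do not say which is more likely.

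The conclusion on mood and anxiety is at stake, together with precision that the entry scores would supply at almost no cost.

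**Working it through.** **The plan's own figure.** The plan gives no sample size for depression or anxiety, so I take the group sizes from Aim 1: "312 in the no medication group and 624 in the 2 fluoxetine groups, for a total sample size of 936". They rest on the assumption that "2/3 of patients who enter the trial will choose to take fluoxetine", on hospitalization of 10% against 5%, and on calculations that "are based on achieving the standards of a power of 0.80 and with an alpha of 0.05".

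- Pooled rate: (0.10 + 2 × 0.05)/3 = 0.0667.
- Controls needed, two-sided, no continuity correction: [1.960 × √(0.0667 × 0.9333 × 1.5) + 0.842 × √(0.09 + 0.0475/2)]² / 0.05² = 311.6, so 312.
- With 624 on fluoxetine the total is 936.

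The stated figure reproduces exactly. Nothing in it is wrong; it supplies the group sizes for what follows.

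**Assumptions, not in the documents.** Entry difference *d* = 0.1 to 0.2 SD; entry-to-follow-up correlation *r* = 0.5 to 0.7; equal SD at both times; everyone supplies a follow-up score; no drug effect; in both groups the follow-up score depends on the recorded entry score through the same line with slope *r*.

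**Standard error of a mean difference, in SD units.** √(1/312 + 1/624) = 0.0693.

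**t-test on follow-up scores.** Spurious difference = *r* × *d*. With *t* = *rd*/0.0693, the chance of a significant result is Φ(*t* − 1.96) + Φ(−*t* − 1.96).

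**t-test on change from entry.** Spurious difference = (*r* − 1) × *d*, with SD √(2(1 − *r*)): 1.000 at *r* = 0.5 and 0.775 at *r* = 0.7. The sign is opposite to that of the follow-up test.

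| *d* | *r* | Follow-up: shift | Follow-up: rejects | Change: shift | Change: rejects |
|---|---|---|---|---|---|
| 0.1 | 0.5 | +0.05 | 11% | −0.05 | 11% |
| 0.1 | 0.7 | +0.07 | 17% | −0.03 | 9% |
| 0.2 | 0.5 | +0.10 | 30% | −0.10 | 30% |
| 0.2 | 0.7 | +0.14 | 52% | −0.06 | 20% |

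For example, at *d* = 0.2 and *r* = 0.7: *t* = 0.14/0.0693 = 2.02, and Φ(0.06) + Φ(−3.98) = 0.52.

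**Adjusting for the entry score.** In simulation (2,000 runs per cell, *d* = 0.2), ANCOVA rejected in 4.9% of runs at *r* = 0.5 and 5.6% at *r* = 0.7 when the recorded entry score carries all of the selection. Residual variance falls by *r*², that is by 25% to 49%.

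**Where adjustment falls short.** Suppose people select on true severity and the score has reliability 0.8 (assumed). At *d* = 0.2, ANCOVA then rejects in 7% of runs (*r* = 0.5) and 11% (*r* = 0.7). The follow-up t-test rejects in 45% and 72%, and the change-score t-test in 17% and 8%. ANCOVA is far better than the follow-up test here, but it is not exact, and at *r* = 0.7 the change score does slightly better.

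**Fewer scores.** If only half of each group supplied a follow-up score (156 and 312, assumed), the standard error is √(1/156 + 1/312) = 0.0981. The same formula gives 8% to 30% for the follow-up test over the same *d* and *r*.

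**The case against.** The strongest reply is that the plan is silent rather than wrong. Section 4 does not assign the t-test to the PHQ-9 or GAD-7 by name, does not say that raw follow-up scores are compared, and leaves room for judgement. A t-test on change from entry, or a chi-square test on a dichotomised score, would fit its wording. This stands as a reading, but it does not rescue the plan. Under the main assumptions the change-score test is also biased, in the other direction, so leaving the choice open lets the sign of the artefact depend on a decision made after the data are seen.

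Second, the size is illustrative. The documents give no SD, entry difference or correlation for either scale, and 312 and 624 were set for hospitalization. In a telephone study of acutely ill patients some scores will be missing, which lowers the rejection rates. This stands in full; the percentages are conditional.

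Third, these are two of five secondary outcomes with no power claim, and the lack of adjustment affects the primary comparison as well. That also stands and limits the priority of this point. What is particular to these outcomes is that an entry measure of the outcome itself is already scheduled and goes unused.

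Two stronger readings are tempting. A reader might infer that self-selection will certainly appear as a drug effect. The documents do not show that: bias needs an actual entry difference, and none is reported. A reader might also infer from the weekly schedule that separate tests will be run each week, multiplying false positives or ignoring the correlation within a person. The Procedures table is a collection schedule; no section plans weekly tests, and a single-week t-test would not violate independence.

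**Conclusion.** The concern holds as a conditional one. Followed as written, the plan compares self-selected groups on depression and anxiety without using the entry score, so an entry imbalance could appear as, or mask, a drug effect. For a 0.1 to 0.2 SD imbalance the false-positive rate of a follow-up-score t-test is about 11% to 52% against a nominal 5%, under the assumptions listed in the working. The omission is certain from the text; the percentages are not.

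Baseline adjustment would remove most of this bias if the recorded score captures the selection, and less if it does not. It cannot deal with unmeasured confounders. It is also incomplete until the treatment variable is defined, because weekly switching means that the group at entry and the current exposure can differ. This should be corrected, ranking below the same lack of adjustment in the primary comparison.

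**What to change.** In section 4, replace the t-test for the PHQ-9 and GAD-7 with one of the following, chosen before the data are examined:

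- ANCOVA at one prespecified week; or
- a linear mixed model for the weekly scores (treatment, week, treatment by week) with one prespecified contrast.

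Either should include the entry score, age and entry setting as covariates.

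Define the treatment variable for the analysis. For example, use choice at entry for the main analysis and time-varying exposure as a sensitivity analysis. For someone who starts later, the entry score is not the score at the time of that decision, so the sensitivity analysis should say which earlier score it adjusts for. State also how scores missing through intubation or death are treated.

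Add a sentence saying that adjustment removes only the measured part of the confounding and that the result remains observational.

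The cost is a paragraph of SAP wording and slightly more analysis. The scores are already scheduled, so no new data, visits or participants are needed.

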#### **Data Safety Monitoring Board**

Interim data analyses will be performed every 3 months and will be presented to a 4 member data safety monitoring board who will prepare a report on the ongoing safety of the clinical trial and consideration of early termination of the study for either benefit or harm per the guidelines of Tyson et al. 2016.

